Over a period of six months, all consecutive consenting patients undergoing on pump coronary bypass grafting surgery requiring sternotomy will be enrolled. The patients will be randomized into two groups. The control group will receive standard of care sternal closure. The study group will receive standard of care sternal closure plus PRP applied to the sternum and the surrounding tissue at the time of closure. Participants and outcome assessors are blinded to group assignment, while surgeons performing the procedure are aware of the intervention. The patients will be followed up for a period of 30 days post-surgery. Wound healing, deep and superficial infection including mediastinitis, and readmissions within 30 days will be documented as primary outcomes. Secondary outcome will be the overall cost burden for the 30-days post-surgery period. Other outcomes will be ICU stay (days), blood transfusions more than 4 units and platelets transfusions more than 4 units.

Discussion

Wound dehiscence and infection in post cardiac surgery period are a significant source of morbidity and mortality. Treatment of these complications may cause prolonged hospitalization, prolonged antibiotic therapy, and revisions of operative procedures. In addition to burden on physical health, the complications associated with cardiac surgery can portend a high financial cost to the patient. The PRP has been shown to decrease the incidence of sternal wound complications following cardiac surgery and routine use of platelet rich plasma has been advocated for all patients undergoing sternotomy for cardiac surgical procedures.

Keywords

Sternal wound infection, Superficial sternal wound infection, Deep sternal wound infection, Surgical site infection, Delayed wound healing, Median sternotomy, Cardiac surgery, Postoperative wound complications, Hospital length of stay, Cost analysis, Platelet rich plasma, coronary artery bypass grafting, wound healing, CABG, readmission rate

INTRODUCTION

Median sternotomy in cardiac surgery is considered to be the gold standard incisional approach for the majority of cardiac operative procedures resulting in a low failure rate and excellent long-term outcomes [1].

Although the incidence of sternal complications after cardiac operations through median sternotomy is relatively low, ranging from 0.4% to 8%, it is associated with a comparatively high mortality rate of up to 47% if left undetected. Indicative of this, the 4-year survival rate of patients diagnosed with sternal complications is 65% compared with 85% in patients who heal without such complications [2]. Median sternotomy can have many complications like wound dehiscence and infection in 0.2 to 8 % of the patients [3, 4]. Some of the serious complications of sternotomy include Deep sternal wound problems DSWP following cardiac surgery, ranging from 0.4–3% in unselected patients [5]. DSWP are rare, but can have serious complications, as it is associated with prolonged hospital stays, long-term antibiotic therapy, multiple surgical procedures, higher mortality and morbidity, and increased patient suffering and costs [6]. This complication can be avoided by using protein rich plasma PRP, since platelets upon activation will excrete growth factors and attractants for tissue stem cells, thus promoting tissue healing [5].

The literature has identified a range of preoperative, perioperative, and postoperative risk factors that are suggested to contribute to the development of sternal complications [2] . Risk factors known for postoperative complications in patients going through cardiac surgery include obesity, bilateral harvesting of the internal mammary artery, unilateral LIMA harvesting, diabetes, steroid therapy, history of active smoking, osteoporosis, and chronic lung diseases [2, 7, 8, 9]. Two studies listed the postoperative requirement for blood products as an independent risk factor for sternal infection [2] . The replacement of blood products may lead to host immunosuppression and increase the risk of sternal infection [2] . Insulin-dependent diabetes mellitus is considered the most serious predisposing factor for deep infections [4]. Given that the IMA is a major blood supply to the sternum, some studies report mobilization of these arteries may lead to sternal hypoperfusion and increase the risk of sternal infection [2].

Complications in the post-surgery period are a significant source of mortality. Treatment of these complications may cause prolonged hospitalization, prolonged antibiotic therapy, and

revisions of operative procedures [10]. Centrifugal-based platelet concentration methods have been developed separating whole blood in a red blood cell (RBC) layer, a platelet rich plasma (PRP) layer and a platelet poor plasma (PPP) layer. The PRP layer also contains a high concentration of leukocytes, which might provide additional protection against infection. Numerous growth factors and chemoattractants are excreted from activated platelets, in sufficient amounts to stimulate vascular proliferation and attract tissue stem cells and in addition platelets also appear to have antimicrobial properties [5]. During the inflammatory phase of wound healing, PRP stimulates the release of growth factors such vascular endothelial growth factor and transforming growth factor beta, which are believed to stimulate cell proliferation, migration, differentiation, and matrix synthesis. These same growth factors can positively affect chondrocyte metabolism, increase chondrogenesis, and improve bone healing and regeneration. PRP wound irrigation was found to be safe and cost-effective, improving healing and leading to a lower incidence of sternal infections [6]. Nowadays, PRP is being used in many specialties to promote speed-up tissue healing and hence less complications . Furthermore, PRP inhibits in vitro the growth of *Staphylococcus aureus*, the most common bacteria responsible for DSWI, and *Escherichia coli*, whereas it was ineffective against *Pseudomonas aeruginosa*, *Enterococcus faecalis* and *Klebsiella pneumoniae* [9]. PRP can be injected in the LIMA bed, hence increasing neovascularization, speeding up the healing process, as a result can avoid deep sternal wound infection, sternal dehiscence and reoperation secondary to postoperative complications.

The PRP has found multiple uses in many fields, including oral, maxillofacial, and plastic surgery [8,10]. In cardiac surgery patients, PRP has been shown to decrease the incidence of sternal wound complications [10]. Although it is not used routinely, some authors suggest regular use of PRP based on preliminary results from studies on reducing complications in patients undergoing cardiac surgery with median sternotomy [8].

Rationale

Postoperative complications cause significant morbidity in post cardiac surgery patients. The PRP has been proposed in clinical trials to reduce the frequency of complications in patients undergoing median sternotomy for cardiac operative procedures. The purpose of our study is to evaluate whether there is any beneficial effect of use of PRP in addition to standard care after on pump CABG, cardiac surgery.

Research Question

Does application of PRP after CABG, cardiac surgery reduce the frequency of sternal wound complications?

Objective

To compare the complication rates of application of PRP in addition to standard sternal wound closure versus standard sternal wound closure alone.

Population

All consecutive patients of age 45 to 72, undergoing CABG, cardiac surgery with median sternotomy will be included in the study.

Intervention

Application of 6 mL of autologous PRP to sternum and soft tissue during sternal closure.

Comparison

The control group will undergo midline sternotomy with a sternal saw blade. The sternum will be closed with a simple interrupted or figure of eight stainless steel wire. The wounds will be closed in a layered manner with absorbable suture and dressed with Steri-Strips, gauze and paper tape. The study group will additionally receive 6 mL of autologous PRP applied to sternum and soft tissue during sternal closure.

Outcome

(i) Primary Outcome;

Primary outcome will be measured as frequency of sternal wound complications in terms of delayed healing, superficial infection, deep infections, and readmission rate including mediastinitis in 30-days period post-surgery.

(ii) Secondary outcome;

Secondary outcome will be the overall cost burden for the 30-days post-surgery period.

(iii) Other outcomes;

Other outcomes will be ICU stay (days), blood transfusions more than 4 units and platelets transfusions more than 4 units within 30 days.

OPERATIONAL DEFINITIONS

1-Cardiac Surgery: Cardiac surgery, also called heart surgery, involves surgical operations performed on the heart to correct life-threatening conditions. The surgery can be either open-heart surgery or minimally invasive surgery depending on the condition to be corrected.

2-PRP: Platelet-rich plasma (PRP) is defined as a portion of the plasma fraction of autologous blood having a platelet concentration above baseline.

3-Study Outcome

Study Outcome will be measured as frequency of sternal wound complications in terms of delayed healing, superficial infection, deep infections, and readmission rate including mediastinitis in 30-days period post-surgery. Secondary outcome will be the overall cost burden for the 30-days post-surgery period. Other outcomes will be ICU stay (days), blood transfusions more than 4 units and platelets transfusions more than 4 units within 30 days.

4- DSWI: DSWI diagnosis will be made, based on the guidelines of the CDC, in patients who developed one or more of the following: [1] positive culture of mediastinal tissue or fluid; [2] clinical evidence of mediastinitis during sternal reoperation; or [3] chest pain, sternal instability, purulent discharge from the mediastinum associated with a positive blood culture. DSWI presenting in the first 30 days after operation will be included in the study.

5- SWI: All the infections will be considered positive that will involve skin and subcutaneous tissue within the first 30 postoperative days, not reaching the sternum, requiring local surgical intervention with regular wound care, accompanied by antibiotic therapy and/or Vacuum Assisted Closure (VAC) therapy.

6- Delayed Healing: Healing is a complex biochemical process of tissue repair after it has been damaged. It has three stages which are inflammation, proliferation and remodelling. Delay in the specific time period or in the biochemical process is called delayed healing. Skin,

subcutaneous tissue or sternum which is unable to heal within two weeks of surgery will be considered delayed wound healing.

7- Readmission: It is defined as any hospital readmission within 30 days of discharge related to the index surgery.

8- ICU stay: Stay that refers to the duration, in days, spent in the intensive care unit, within 30 days postoperatively.

9- Blood transfusion: It is defined as the requirement of more than 4 units of packed red blood cells (PRBC) or platelets within 30 days postoperatively.

Hypothesis

Administration of platelet rich plasma during sternal wound closure reduces the frequency of complications in the 30-days post-surgery period.

MATERIAL AND METHODS

Study Design

Randomized control trial

Study Setting

The Department of Cardiac Surgery, Cardiac Center, Pakistan Institute of Medical Sciences (PIMS), Islamabad.

Duration

06 months after acceptance of synopsis

Sample selection;

Inclusion criteria

Patients from 45 to 72 years of age, undergoing on pump CABG,

cardiac surgery with median sternotomy.

Patients who provide consent.

Exclusion criteria

- BMI less than **18.5** or more than **24.9**
- Bilateral harvesting of the internal mammary artery,
- Steroid therapy,
- Known Diabetic,
- Active smoker,
- Osteoporosis,
- Chronic lung disease,
- CPB time more than 72.5 minutes
- Platelet Rich Plasma cannot be obtained.
- Patients who are not candidates for blood bank donations.

Sample size

The sample size has been calculated by using WHO size calculator with the statistical assumptions as following:

(Level of significance = 5%), (Power of test = 80%), (Population standard deviation = 3.0)

(Anticipated population, rate of oedema and infiltration in prp group, P1= 18%)

Anticipated population, rate of oedema and infiltration in control group, P2= 44% Sample size comes out to be 49 cases in each study group and a total of 98 patients will be included in the study.

Sampling Technique

Participants will be recruited using non-probability consecutive sampling and randomly assigned to one of two groups.

Data Collection Procedure

The study protocol will be first submitted for approval to the hospital ethics committee and Advance Research committee. A written informed consent will be taken from all parents/ caretakers. The subjects fulfilling inclusion will be enrolled from Cardiac Center. Participants will be recruited using non-probability consecutive sampling and randomly assigned to one of two groups. The antibiotic prophylaxis will be given 60 min before incision. The preoperative antibiotics protocol and glycemic management protocol will be standard and will remain the same for all patients throughout the study. Patients will be given general anesthesia. This will ensure that they are asleep and pain free through the whole surgery. An incision of 8- to 10-inch will be made in the chest. A midline sternotomy with a sternal saw blade will be done. Bleeding sites will be secured followed by pericardectomy. Once the heart is visible, cannulation will be done and the patient will be connected to a heart-lung bypass machine. The machine will move blood away from the heart so that the surgeon can operate. Surgery will be performed according to local guidelines. Patients will be heparinized using an initial dose of 300 IU/kg unfractionated heparin. During surgery the activated clotting time (ACT) will be maintained at least 480 s. All patients undergoing sternotomy will be included in the study including emergencies, reoperations, ventricular assist device implantations, heart transplants, aortic dissections and standard operations (i.e. coronary artery bypass grafting and valve repairs or replacements). Following sternotomy, the use of bone wax on the sternum will be avoided, as this might form an intrasternal barrier and interfere with PRP augmented healing. Targeted flow rates during cardiopulmonary bypass were 2.6 L/min/m² , yielding a venous saturation of 70–80%. After heparin reversal is achieved with protamine, all the bleeding spots will be identified and stopped i.e. haemostasis will be secured. The control group will undergo midline sternotomy with a sternal saw blade. The sternum will be closed with a simple interrupted or figure of eight stainless steel wire. The wounds will be closed in a layered manner with absorbable suture and dressed with Steri-Strips, gauze and paper tape. The study group will additionally receive 6 mL of autologous PRP applied to sternum and soft

tissue during sternal closure. Participants and outcome assessors will be blinded to group assignment, while surgeons performing the procedure will be aware of the intervention

Primary outcome will be measured as frequency of sternal wound complications in terms of delayed healing, superficial infection, deep infections, and readmission rate including mediastinitis in 30-days period post-surgery. Secondary outcome will be the overall cost burden for the 30-days post-surgery period. Other outcomes will be ICU stay (days), red cell concentrate (RCC) more than 4 units and platelets transfusions more than 4 units.

All the information will be entered on the predesigned Performa by the researcher himself to comply with the study protocol attached as **Annexure-I**.

Data Analysis

Quantitative variables (age, hospital stay, ICU stay, cost) will be summarized as mean \pm SD or median (IQR) and compared using t-test or Mann-Whitney U test. Categorical variables (superficial/deep wound infections, delayed healing, readmissions, transfusion requirements, residence (urban\rural), education status and socioeconomic background (low\middle) will be reported as counts and percentages and compared using chi-square or Fisher's exact test. A p-value <0.05 will be considered significant. Missing data will be handled using complete case analysis. All analyses will be performed using [SPSS/R].

Ethical Considerations

From ethical point of view:

- Those patients will be included in the study that will be willing to participate in the study.
- A written informed consent will be taken from the patients and they will be ensured that their confidentiality will not be breached.
- There will be no compromise on the standard care and treatment for study purposes.

References

- [1] Reser, Diana, et al. "Median sternotomy." *Multimedia manual of cardiothoracic surgery: MMCTS 2015* (2015).
- [2] Balachandran, Sulakshana, et al. "Risk factors for sternal complications after cardiac operations: a systematic review." *The Annals of thoracic surgery* 102.6 (2016): 2109-2117.
- [3] Patel, Amit N., et al. "Evaluation of autologous platelet rich plasma for cardiac surgery: outcome analysis of 2000 patients." *Journal of cardiothoracic surgery* 11.1 (2016): 1-6.
- [4] Heilmann, Claudia, et al. "Wound complications after median sternotomy: a single-centre study." *Journal of cardiothoracic surgery* 13.1 (2018): 1-6.

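### The cost outcome starts counting after surgery, so read literally it leaves out the cost of PRP, which only the study arm receives, during sternal closure

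*Protocol*

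**What the plan says.** Cost is the only outcome labelled secondary. The opening summary, Outcome (ii), item 3 of the Operational Definitions and the Data Collection Procedure all define it in the same way: "Secondary outcome will be the overall cost burden for the 30-days post-surgery period". The opening summary uses the same period for follow-up: "The patients will be followed up for a period of 30 days post-surgery".

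The Intervention section places the treatment inside the operation: "Application of 6 mL of autologous PRP to sternum and soft tissue during sternal closure". The Comparison section makes it an addition in one arm to a closure that both arms share: "The study group will additionally receive 6 mL of autologous PRP applied to sternum and soft tissue during sternal closure".

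The Data Analysis section treats cost as one more quantitative variable: "Quantitative variables (age, hospital stay, ICU stay, cost) will be summarized as mean" with SD, or as median with IQR, and compared by t-test or Mann-Whitney U test. The protocol gives no list of cost items, no costing perspective and no price for PRP. It nowhere says that PRP or index-operation costs are added to the total.

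**The concern.** The only planned difference between the arms is PRP. Its application is finished before the post-surgery period begins, and collection and processing must come before application, so they too fall before the window. A cost total that starts after surgery would credit the PRP arm with any later saving and not charge it for PRP.

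Leaving out operative costs that both arms share does little harm to a comparison of arms. Leaving out a cost that falls on one arm moves the difference by that amount. Randomisation, blinded assessment or a larger sample cannot correct this, because it lies in the outcome definition.

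At stake is how the cost result can be used. The opening summary reports that routine PRP has been advocated for all sternotomy patients, and the Introduction describes PRP irrigation as cost-effective. A reader would take a cost result from this trial as evidence on whether PRP is worth adding.

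**Working it through.** **1. The plan's own figure.** The protocol states no figure for cost; the only one to reproduce is the sample size. The inputs, from the Sample size section, are 5% significance, 80% power, 18% with PRP and 44% in control. With the pooled two-sided formula and no continuity correction, and a mean rate of 0.31:

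n = [1.96 × √(2 × 0.31 × 0.69) + 0.842 × √(0.18 × 0.82 + 0.44 × 0.56)]² / 0.26² ≈ 48.5, rounded up to 49 per arm.

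This matches the stated 49 per group (98 in total); power at 49 is 80.4%. The point about cost does not depend on it.

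**2. Inputs for cost.** The protocol gives neither p (the per-patient cost of PRP in the study arm) nor C (the extra cost of one complication). The same section lists a standard deviation, "Level of significance = 5%), (Power of test = 80%), (Population standard deviation = 3.0", but with no variable or unit, so it cannot serve as a cost SD. The results below are therefore in relative terms.

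**3. Bias in the mean difference (PRP minus control).** Let d be the absolute reduction in complications, and assume that complications are the only source of a post-surgery cost difference.

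- Total cost, PRP counted: p − dC
- Literal post-surgery window: −dC
- Bias: −dC − (p − dC) = −p, in favour of PRP for any p above zero
- The expected sign is wrong when p − dC > 0, that is, when p > dC

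| d | Basis | Sign wrong when | At an assumed p = 0.05C: total cost | At an assumed p = 0.05C: literal window |
|---|---|---|---|---|
| 0.04 | Assumed fall from 8% (top of the Introduction's range) to 4% | p > 0.04C | +0.01C | −0.04C |
| 0.26 | 0.44 − 0.18, Sample size section | p > 0.26C | −0.21C | −0.26C |

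The second row uses the protocol's only planning contrast. It is stated for a different event, "rate of oedema and infiltration in prp group, P1= 18"%, so it is an imperfect stand-in for sternal wound complications. The bias is p in both rows; only its effect on the sign differs.

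**4. Effect on the test.** Suppose true total costs are equal, with 49 per arm, and an omitted PRP cost of c standard deviations of cost. The chance of a significant result favouring PRP (two-sided 5%, normal approximation) is Φ(c / √(2/49) − 1.96):

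| c (SD of cost, assumed) | Chance of a significant result favouring PRP |
|---|---|
| 0 | 2.5% |
| 0.1 | 7.1% |
| 0.25 | 23.5% |
| 0.5 | 69.7% |
| 0.75 | 96.0% |

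The values of c are a range, not estimates.

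**The case against.** The strongest reply is that the exclusion is inferred. The outcome is called overall, the analysis section says simply cost, and both words are compatible with one hospital bill running to day 30. The Performa (Annexure-I) is not shown, a statistical analysis plan may exist, and itemising costs is often left to such documents. This stands in part: a reader might infer that the protocol says PRP will go uncosted, and it does not. But the window is fixed in the protocol, is the same all four times, and qualifies the word overall. An analysis that follows it would leave PRP out.

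Second, the research question, objective and hypothesis concern complications only, and the stated motive for cost is the financial burden of complications. Downstream cost alone is a coherent quantity for that purpose. This stands too, and is a reason to keep it as a reported component. It does not make it a fair overall comparison of the arms.

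Third, a reader might infer that PRP is prepared during the operation and in the study arm alone. The protocol documents only application as arm-specific. It does not say when blood is drawn or processed, and the exclusion of patients in whom PRP cannot be obtained is not limited to one arm. If control patients also had PRP prepared, those costs would fall on both arms of the trial. The cost of using PRP would still have to be charged to the PRP strategy.

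Fourth, the omitted amount is nearly constant per treated patient and could be added at analysis. That is so if a unit cost is recorded, which the protocol does not plan.

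**Conclusion.** The point holds as a defect in the outcome definition. On its literal wording, the sole secondary outcome omits the cost of applying PRP, and of preparing it where only the study arm bears that cost. The mean cost difference is then biased towards PRP by p. The direction is clear for any positive p; the size in money cannot be found from the protocol. Whether the expected sign is wrong depends on p against dC: above 4% of C at the assumed d of 0.04, but only above 26% of C at the protocol's own planning rates. The documents do not show that the sign will be wrong.

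A reader might also infer that this outcome would show PRP as cost-neutral or cheaper whenever complications are equal or fewer. That goes too far. It holds at most in expectation, and only if complications drive the post-surgery difference. ICU stay, transfusion and sampling variation with 49 per arm could produce either result.

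The primary outcome, the randomisation and the sample size are unaffected. The definition should be corrected before cost data are collected.

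**What to change.** Define the secondary outcome as total cost from the index operation to day 30 after surgery in both arms. For patients allocated to PRP, count its collection, processing, consumables and application, and include collection or processing done before the operation. Report post-surgery cost as a separate component, so that the downstream burden of complications remains visible. Use the same wording in all four places where the outcome is defined. If the sponsor already means to count PRP, the same change makes that explicit.

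The cost is a revised sentence in the outcome definition and one extra cost line on the Performa. The sample size does not change. The downside for the sponsor is a cost result less favourable to PRP, by p per patient, than the literal window would give.

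### Transfusion is compared only as more or not more than 4 units, which discards a material part of the unit count, and its definitions disagree on the time window and on how the products are combined

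*Protocol*

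**What the plan says.** Transfusion appears in five places in the protocol, always with the cut at 4 units and never with a reason for it.

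- **Outcome, (iii) Other outcomes:** "blood transfusions more than 4 units and platelets transfusions more than 4 units within 30 days". Red cells and platelets are two outcomes, and the window is 30 days with no stated start. Operational Definitions, item 3, repeats this.
- **Operational Definitions, item 9:** "requirement of more than 4 units of packed red blood cells (PRBC) or platelets within 30 days postoperatively". The two products are joined by *or*, and the window is postoperative.
- **Data Collection Procedure:** "red cell concentrate (RCC) more than 4 units and platelets transfusions more than 4 units". The products are separate and the sentence gives no window.
- **Summary before the Discussion:** the same two outcomes, again without a window in the outcome sentence, although 30-day follow-up is mentioned earlier in the paragraph.
- **Data Analysis:** "Categorical variables (superficial/deep wound infections, delayed healing, readmissions, transfusion requirements" and further items are reported as counts and percentages and compared by chi-square or Fisher's exact test. The other list reads "Quantitative variables (age, hospital stay, ICU stay, cost) will be summarized as mean" and so on, with the t-test or Mann-Whitney test. Transfused units are not in it.

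**The concern.** A patient can be classed as above 4 units only if someone has counted the units. The plan then reduces that count to yes or no. A patient given no units and one given 4 count the same, and so do patients given 5 and 12. If typical use is low, few patients cross the line and the comparison rests on a handful of events. A non-significant result could then be read as evidence that the PRP procedure does not affect blood use, when the test had little chance of showing it. The Introduction names the need for blood products after surgery as a risk factor for sternal infection, so the variable bears on the trial's question.

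Separately, item 9 can be read as one combined outcome with a postoperative window, while the outcome list has two outcomes and a window without a start. Two analysts could produce different transfusion tables from the same data.

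**Working it through.** **The plan's own figure.** The protocol gives no expected transfusion rate or unit distribution. Its only design figure is 49 per arm, for 18% against 44% with oedema and infiltration. With a two-sided 5% level, 80% power, pooled variance and no continuity correction:

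n = [1.96·√(2·0.31·0.69) + 0.8416·√(0.18·0.82 + 0.44·0.56)]² / 0.26² = (1.282 + 0.528)² / 0.0676 = 48.5, rounded up to 49.

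This reproduces. It concerns another endpoint and supplies only the number of patients used below.

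**Step 1: information kept by the cut.** Assumed, not in the documents: units follow a Poisson or negative binomial distribution (k = 2 or k = 1; smaller k means more spread) with mean μ of 1 to 4. Let p = P(more than 4 units). The information about log μ is

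- from the cut: (dp/d log μ)² / [p(1 − p)]
- from the count: μ (Poisson) or μ/(1 + μ/k) (negative binomial).

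Example, Poisson with μ = 1: p = 0.00366 and dp/d log μ = μ·P(X = 4) = e⁻¹/24 = 0.01533. The cut gives 0.01533² / (0.00366 × 0.99634) = 0.064 and the count gives 1, so 6% is kept.

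| Share kept | μ = 1 | μ = 2 | μ = 3 | μ = 4 |
|---|---|---|---|---|
| Poisson | 6% | 33% | 56% | 65% |
| k = 2 | 26% | 56% | 65% | 63% |
| k = 1 | 40% | 63% | 65% | 61% |

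The loss therefore runs from 35% to 94%. It exceeds half in four of the twelve cells: Poisson means 1 and 2, and both negative binomials at mean 1. In the other eight it is 35% to 44%.

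**Step 2: power with 49 per arm.** Two-sided 5%, negative binomial counts, 3,000 simulated trials per row:

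| Means (k) | Above 4 units | Mann-Whitney on units | Chi-square on cut | Fisher on cut |
|---|---|---|---|---|
| 1.0 v 2.0 (2) | 1.8% v 10.9% | 79% | 54% | 26% |
| 1.5 v 2.5 (2) | 5.6% v 17.1% | 61% | 46% | 29% |
| 1.0 v 1.7 (1.5) | 2.3% v 8.5% | 49% | 32% | 10% |
| 2.0 v 3.0 (1) | 13.2% v 23.7% | 30% | 27% | 19% |

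Summing over all possible tables for the first row gives 52% (chi-square) and 25% (Fisher), in line with the simulation. The plan allows either test. Expected numbers above the cut per arm are 49 × (1.8% + 10.9%)/2 = 3.1 in the first row and 49 × (2.3% + 8.5%)/2 = 2.6 in the third, where Fisher would usually be chosen. In the second and fourth rows they are 5.6 and 9.0, where chi-square would serve.

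**Step 3: a second set of assumptions.** Ratio of means 0.6, control mean 1 to 4, the three distributions of step 1, 4,000 runs each. Mann-Whitney against chi-square (Fisher):

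- Poisson, mean 2: 86% v 20% (3%)
- Poisson, mean 4: 99% v 92% (87%)
- k = 2, mean 2: 57% v 38% (16%)
- k = 1, mean 4: 46% v 43% (35%)

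The count had the higher power in all twelve scenarios, by 3 to 67 percentage points over chi-square.

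**Step 4: the definitions side by side.**

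| Place | Products | Window |
|---|---|---|
| Outcome (iii); Definitions item 3 | separate | 30 days, no start |
| Definitions item 9 | joined by *or* | 30 days, postoperative |
| Data Collection Procedure; summary | separate | none in the sentence |

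**The case against.** **High use is a recognisable severity endpoint, and this is third-tier.** True. Transfusion stands below the primary and secondary outcomes and drives neither the hypothesis nor the sample size. That lowers the weight of the point. It does not justify analysing only the cut when the count has to be known.

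**The count would often fail too.** Also true. For means of 1.0 against 1.5 units (k = 2) Mann-Whitney has about 34% power, and for 1.5 against 2.0 about 24%. The change improves the comparison but does not make it well powered.

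Four stronger readings are tempting, and the documents do not support them.

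- *Most of the information is lost.* That holds only for low mean use, and the protocol gives no distribution.
- *A finding of no difference is close to preordained.* This depends on low use and on Fisher rather than chi-square. A reader may infer low use from the exclusions, such as "CPB time more than 72.5 minutes". But the Data Collection Procedure says emergencies, reoperations, transplants and aortic dissections are included. Those two passages conflict and must be reconciled, so the case mix cannot be taken as settled.
- *Leaving out units given in theatre biases the comparison.* The words "within 30 days postoperatively" are attached to transfusion only in item 9. PRP is applied at closure and cannot affect earlier units, so counting these might mainly add noise. Autologous PRP needs a blood draw beforehand, but its time and volume are not stated. An effect of the draw on transfusion in theatre is possible, not shown.
- *These are the only outcomes that could reveal blood use.* The 30-day cost outcome may also reflect it.

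**Conclusion.** The point stands as a minor one. The protocol fixes a binary outcome and a categorical test for "transfusion requirements", and this discards a material part of a count that must be made to apply the cut. The loss is about 35% to 94% for assumed mean use of 1 to 4 units. The gain in power from analysing units ranges from 3 points to more than 60 over chi-square. These sizes rest entirely on the assumed distributions and differences; the direction was the same in every scenario. The inconsistency of window and product definition needs no assumption, since it stands in the text. Nothing here touches the primary result or the 49 per arm.

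**What to change.** 1. Define two other outcomes: number of red-cell units and number of platelet units. Summarise each as median (IQR) by arm, and add both to the quantitative variables in Data Analysis, compared with the Mann-Whitney test already listed there.
2. Keep more than 4 units as a supplementary percentage for each product.
3. Reconcile the summary, Outcome (iii), Operational Definitions items 3 and 9 and the Data Collection Procedure to one window with a stated start and end, the same in both arms. Say explicitly whether units given in theatre count.
4. Remove the *or* in item 9, or say that a combined outcome is meant in addition to the separate ones.

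The cost is small. The data form (Annexure-I, not shown) must hold the number of units of each product and not only yes or no. If the chosen window starts before the end of surgery, units given in theatre must be recorded as well. No extra patients or visits are needed.
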